## SYNOPSIS

Name of Sponsor/Company:	Archigen Biotech Ltd	
Name of Finished Product:	SAIT101 (proposed rituximab biosimilar)	
Name of Active Ingredient:	Rituximab	
Title of Study:	A Randomized, Double-blind, Parallel Group, Multicenter Study to Compare the Pharmacokinetics, Pharmacodynamics, Safety, and Efficacy of SAIT101 versus MabThera ® versus Rituxan ® in Patients with Rheumatoid Arthritis (RA).	
Protocol No:	AGB001	Phase: I/III
Investigators:	Approximately 70 Investigators	
Study centers:	Approximately 70 study centers globally	
Objectives:		
Primary Objective:		
The primary objective of the study is to compare the pharmacokinetics (PK) of SAIT101 (proposed rituximab biosimilar) versus rituximab licensed in the European Union (hereafter designated MabThera ® , brand name in EU) versus rituximab licensed in the United States (hereafter designated Rituxan ® , brand name in US) in patients with rheumatoid arthritis (RA).		
Secondary Objectives:		
The secondary objectives of the study are to compare the safety, additional PK, pharmacodynamics (PD), efficacy, tolerability, and immunogenicity of SAIT101 versus MabThera ® versus Rituxan ® in patients with rheumatoid arthritis (RA).		
Methodology:		
This is a multicenter, randomized, double-blind, parallel group study to compare the PK, PD, safety, efficacy, tolerability, and immunogenicity of SAIT101 versus MabThera ® versus Rituxan ® in patients with RA. This study consists of Part A up to 24 weeks followed by Part B up to Week 52 that also collects transition data in patients eligible for a second course of treatment.		
It is planned to randomize approximately 282 patients.		
The regular study duration per individual patient will be 52 weeks from the start date of the first course.		
Overview of Study Design		
Part A - First Course: Patients will be randomized in a 1:1:1 ratio to receive one course of SAIT101 (n=94) versus Rituxan ® (n=94) versus MabThera ® (n=94).		
Part B - Second Course:		
Eligible patients in the SAIT101 arm will receive the second course of SAIT101 treatment at Week 24 and Week 26.		
Eligible patients in the MabThera ® arm will receive the second course of MabThera ® treatment at Week 24 and Week 26.		
Eligible patients in the Rituxan ® arm will be randomized in a 1:1 ratio to receive SAIT101 or Rituxan ® treatment at Week 24 and Week 26.		
Study Population		
Patients with RA who have had an inadequate response to at least 3 months' treatment (according to the approved treatment and dosage) or intolerance (at Investigator's discretion and/or experience of severe adverse event [AE] or toxicity such as infusion related reaction, hypersensitivity, anaphylaxis or severe toxicity) to anti-tumour necrosis factor (TNF) therapy.		

Name of Sponsor/Company:	Archigen Biotech Ltd
Name of Finished Product:	SAIT101 (proposed rituximab biosimilar)
Name of Active Ingredient:	Rituximab

**Screening and Baseline**

All the Screening assessments should be performed within 30 days prior to randomization on Day 1 (Visit 2, Baseline), except in patients who require prophylaxis of latent tuberculosis or a washout of current anti-TNF medication or other biologic and non-biologic disease-modifying anti-rheumatic drug (DMARD) treatment (except methotrexate [MTX]). For these patients the Screening Period may be extended to allow for the washout required, but will not exceed 60 days. In these patients all Screening assessments must be performed within 30 days prior to randomization with the exception of the informed consent and chest X-ray.

**Treatment Regimen**

Each patient will receive first course which includes two intravenous (i.v.) 1,000 mg study drug infusions: one on Day 1 (Visit 2) and the second on Day 15 (Visit 5). Patients will receive an anti-pyretic and an anti-histamine, e.g., paracetamol and diphenhydramine or equivalent, 30 to 60 minutes before each infusion, plus 100 mg i.v. methylprednisone within 30 minutes prior to each infusion.

Patients with an inadequate response (<50% improvement from Baseline in both the swollen and tender joint counts) at Week 24 (Visit 12), will be eligible to receive the second course of two 1,000 mg i.v. infusions (one at Week 24 and the second infusion at Week 26 [14 days later]) of study drug.

On Day 1 and Day 15 (first and second infusions) blood PK samples and PD (CD19+ B-cell) samples will be collected before and 3 hours after the start of infusion and immediately (within 10 minutes) before and 1 hour after the end of infusion, at 48 hours after the start of each infusion (Days 3 and 17).

The PK/PD samples will also be taken at Weeks 4, 8, 12, 16, 20, and 24 to estimate elimination.

Blood PD samples will be additionally collected simultaneously at Weeks 36 and 52.

The main efficacy variable change from baseline in DAS28 (Disease Activity Score) will be evaluated on completion of 24 weeks of study assessments.

- All patients will be followed up for up to 52 weeks from the start date of the first infusion.
- Patients will attend the study center approximately every 12 weeks during Part B, from the start date of the second course of infusions. Patient who are not eligible for the second course of study treatment will also attend all visits until week 52.

Name of Sponsor/Company:	Archigen Biotech Ltd	
Name of Finished Product:	SAIT101 (proposed rituximab biosimilar)	
Name of Active Ingredient:	Rituximab	
	
 
To prevent missing data in important supportive efficacy and safety analysis, patients who discontinued study treatment, will also attend all visits until week 52.
 
Patients, Investigators, joint assessor and other study personnel (except pharmacist) will remain blinded to the treatments throughout the entire Treatment Period (52 weeks).
 
An interim analysis of 10 patients per arm (30 patients in total) of safety data collected up to Week 4 and 20 patients per arm (60 patients in total) of safety data collected upto Week 12 are planned.
 
The study will be unblinded at Week 24 and an interim CSR will be prepared based on the 24-week data of all patients. The investigators and patients will remain blinded to treatment assignment during the post Week 24 follow-up period.
 
An independent Data Safety Monitoring Board (DSMB) will be assigned for this study. The DSMB will review available study data at pre-specified time points as outlined in the DSMB charter.
 
Investigators will be instructed to monitor the patients throughout the study to detect the first symptoms or neurological signs suggestive of progressive multifocal leukoencephalopathy (PML, i.e., cognitive or visual disorders, hemiparesis, confusion or behavior disorders). If the patients develop new neurological signs or symptoms they should be evaluated for PML. Neurological warning signs include: major changes in vision, unusual eye movements; loss of balance or coordination; and disorientation or confusion. Any patient who is suspected of developing PML will be discontinued from the study treatment and the AE will be followed closely, at the discretion of the Investigator.
 
	
Number of patients:	Approximately 282 patients will be randomized into the study, at approximately 70 investigative centers.	
Diagnosis and main criteria for inclusion:	
Male and female patients aged between 18 and 80 with severe RA who have had an inadequate response to at least 3 months' treatment (according to the approved treatment and dosage) or intolerance (at Investigator's discretion and/or experience of intolerable adverse events or toxicity such as infusion related reaction, hypersensitivity, anaphylaxis or severe toxicity) to anti-TNF therapy (experience of severe adverse event or toxicity).
 
Patients have to be on a stable weekly dose of MTX, 7.5 – 25 mg/week at least 12 weeks, including the last 4 weeks prior to Day 1 at a stable dose (lower doses of MTX <10 mg/week are only permitted if patients have documented evidence of intolerance to higher doses of MTX).
	
Test product, and comparator, dose and mode of administration:	
1,000 mg (10 mg/mL) SAIT101 or Rituxan® or MabThera® for i.v. infusion.
 
In Part A, each patient will receive one course of two 1,000 mg study drug infusions: one infusion on Day 1 and the second on Day 15.
 
In Part B, patients with an inadequate response (<50% improvement from Baseline in swollen and tender joint counts at Week 24 [Visit
	

Name of Sponsor/Company:	Archigen Biotech Ltd	
Name of Finished Product:	SAIT101 (proposed rituximab biosimilar)	
Name of Active Ingredient:	Rituximab	
	
12]) will be eligible for a further course of two 1,000 mg drug infusions: one infusion at Week 24 and the second one at Week 26:
 
 
• Eligible patients in the SAIT101 arm will receive additional SAIT101 treatment at Week 24 and Week 26.
 
• Eligible patients in the MabThera® arm will receive additional MabThera® treatment at Week 24 and Week 26.
 
• Eligible patients in the Rituxan® arm will be randomized in a 1:1 ratio to receive SAIT101 or Rituxan® treatment at Week 24 and Week 26.
 
	
Method of administration:	
Patients will receive an anti-pyretic and an anti-histamine, e.g., paracetamol and diphenhydramine, or equivalent 30 to 60 minutes before each infusion, plus 100 mg i.v. methylprednisone at least 30 minutes prior to each infusion.
 
The Day 1 infusion rate (both first and second courses) of SAIT101 or MabThera® or Rituxan® will be 50 mg/hour; after the first 30 minutes, it can be escalated in 50 mg/hour increments every 30 minutes, to a maximum of 400 mg/hour. If there has been no infusion related reaction on Day 1, the Day 15 infusion (both first and second courses) can be started at 100 mg/hour and increased by 100 mg/hour increments at 30 minute intervals, to a maximum of 400 mg/hour.
 
Drug infusions will take place under the close supervision of an experienced physician, and in an environment where full resuscitation facilities are immediately available.
	
Duration of study:	Total study duration up to 52 weeks for each patient, including Baseline, Part A and Part B.	

Main criteria for evaluation:
 
Pharmacokinetics
 
Primary PK endpoints
 
 
• Area under the concentration-time curve from time 0 (immediately predose on Day 1) to last quantifiable concentration (<math>AUC_{0-t}</math>)
 
• AUC from time 0 to infinity (<math>AUC_{0-\infty}</math>)
 
• AUC from time 0 to Day 15 prior to infusion (<math>AUC_{0-d15}</math>)
 
• Maximum concentration (<math>C_{max}</math>) after Day 15 infusion
 
• Trough concentration (<math>C_{trough}</math>) before the second infusion on Day 15
 
 
Secondary PK endpoints
 
 
• AUC from Week 2 to Week 24 (<math>AUC_{w2-w24}</math>)
 
• AUC from time 0 (immediately predose on Day 1) to Week 12 (<math>AUC_{0-w12}</math>)
 
• Time of maximum concentration (<math>T_{max}</math>) post infusion on Day 15
 
• Systemic clearance (CL)
 
• Volume of distribution (<math>V_D</math>)
 
• Terminal half-life (<math>t_{1/2}</math>)
 
		

EfficacyMain Efficacy endpoint

- Change from Baseline in DAS28 at Week 24

Other Efficacy endpoints

- Change from Baseline in DAS28 at Weeks 8, 16, 36, and 52
- ACR20 response rates at Weeks 8, 16, 24, 36, and 52
- ACR50 response rate and ACR70 response rate at Weeks 8, 16, 24, 36, and 52
- Individual components of the ACR improvement criteria on Day 1 and at Weeks 8, 16, 24, 36, and 52
  - Swollen and tender joint count (the 66/68 joint count system)
  - Patient's assessment of pain (assessed on 1 to 100 mm Visual Analogue Scale [VAS])
  - Physician's global assessment of disease activity (assessed on 1 to 100 mm VAS)
  - Patient's global assessment of disease activity (assessed on 1 to 100 mm VAS)
  - Patient's assessment of disability (Health Assessment Questionnaire-Disability Index; HAQ-DI)
  - C-reactive protein level.
- Change from Baseline in DAS28-CRP to Weeks 8, 16, 24, 36, and 52
- Major clinical response (continuous ACR70 for at least 24 weeks)
- Clinical remission (defined by SDAI <3.3) at Weeks 8, 16, 24, 36, and 52
- Proportion of patients with European League Against Rheumatism (EULAR) response (good response, moderate response or no response) at Weeks 8, 16, 24, 36, and 52

Pharmacodynamics

The CD19+ B cell count at the pre-infusion on Day 1 will be used as Baseline. The following PD variables will be calculated:

- Depletion of CD19+ B cell count at Week 24
- Time needed to B cell depletion
- Duration of CD19+ B cell depletion
- % CD19+ B-cell count vs. baseline at Week 24
- AUC of CD19+ B-cell count change at Week 24
- Change from Baseline in CD19+ B cell count during the study period
- Change from Baseline in immunoglobulin (Ig) IgG, IgM, and IgA levels at Weeks 24 and 52
- Change from Baseline in CRP levels at Weeks 8, 16, 24, 36, and 52

Safety

- Serious adverse events (SAEs), adverse events (AEs), adverse drug reactions (ADRs)
- Vital signs
- Clinical laboratory parameters including hematology, chemistry and urinalysis
- Physical findings
- Concomitant medication, incidence of rescue medication, where rescue medication is defined as the use of non-biologic DMARDs after Week 16 of the study
- B cell recovery measured by a CD+19 B cell count after Week 24

Immunogenicity (HACA and Neutralizing Antibody)

- Incidence of human anti-chimeric antibodies (HACA) and neutralizing antibody at Day 1 predose and at Weeks 1, 2, 4, 12, 16, 24, 36, and 52

**Statistical methods:**Pharmacokinetic Analyses

Name of Sponsor/Company:	Archigen Biotech Ltd	
Name of Finished Product:	SAIT101 (proposed rituximab biosimilar)	
Name of Active Ingredient:	Rituximab	

The PK analysis will be performed on the PK Analysis Set. The PK parameters, <math>AUC_{0-t}</math>, <math>AUC_{0-\infty}</math>, <math>AUC_{0-d15}</math>, <math>C_{max}</math> after the second infusion on Day 15 and <math>C_{trough}</math> before the second infusion on Day 15 will be considered the co-primary PK endpoints. All other PK endpoints will be regarded as secondary.
 
The statistical analysis of the <math>\log_e</math>-transformed primary endpoints will be based on an analysis of variance model. The difference in least squares means between each of the three pairs (SAIT101 vs. MabThera®, SAIT101 vs. Rituxan®, and MabThera® vs. Rituxan®) and the associated 90% confidence interval (CI) will be determined. Back transformation will provide the ratio of geometric means and 90% CI for this ratio. Equivalence will be concluded if the 90% CI for the ratio of geometric means of each of the three pairs for primary endpoints are completely contained within the acceptance interval of 0.8 to 1.25.
 
Descriptive statistics (N, mean, standard deviation, coefficient of variation (CV), minimum, median, and maximum) will be used to summarize serum concentration data by treatment at each planned sampling time point. Concentrations that are below the lower limit of quantification will be assigned a value of 0 for the purposes of computing descriptive statistics. Serum PK parameters calculated from the concentration-time data will also be summarized by treatment using descriptive statistics.
 
Plots of the mean and individual serum rituximab concentrations over time for SAIT101 and MabThera® or Rituxan® will be provided following i.v. infusions.
 
Pharmacodynamic Analyses
 
Observed, change from Baseline, and percent change from Baseline in CD19+ B cell counts, depletion incidence for CD19+ B cell counts, time needed to B cell depletion, duration of CD19+ B cell depletion and IgG, IgM, IgA, CRP levels will be summarized using descriptive statistics.
 
Efficacy Analyses
 
The change from Baseline in DAS28 at Week 24 will be considered the main efficacy endpoint.
 
Two-sided 95% CI for the difference between SAIT101 and MabThera® in DAS28 change from Baseline at Week 24 will be computed from an analysis of covariance using Baseline DAS28 as covariate and treatment as model factors. Equivalence will be concluded if the 95% CI for the mean difference for main endpoint is completely contained with the equivalence margin of -0.6 to 0.6. Both of the per protocol (PP) set and full analysis set (FAS) will be considered as the efficacy analysis population and no missing data will be imputed for the efficacy analyses in FAS.
 
Continuous variables will be summarized using N, mean, standard deviation, minimum, median, and maximum. Categorical variables will be summarized using frequency counts and percentages.
 
Safety Analyses
 
All reported terms for AEs will be coded using the Medical Dictionary for Regulatory Activities (MedDRA). No statistical testing will be performed for AEs. For all AE and SAE tables, patients will be counted at most once for each Preferred Term (PT) and each System Organ Class (SOC). Adverse events will be summarized by the number and percentage of patients experiencing events by SOC, PT and severity.
 
Changes in vital signs and clinical laboratory measurements will be summarized descriptively by visit. Other safety variables will be summarized and listed.
 
Immunogenicity Analyses
 
Incidence of HACA and neutralizing antibody and summary of counts of antibodies per patient at prior first dose on Day 1 and at Week 1, 2, 4, 12, 16, 24, 36 and 52 will be summarized overall and by treatment group.
 
Interim Analysis
 
Interim Analyses of 10 patients per group (30 patients in total) of safety data collected up to Week 4 and 20 patients per group (60 patients in total) of safety data collected up to Week 12 are planned.
		

Name of Sponsor/Company:	Archigen Biotech Ltd	
Name of Finished Product:	SAIT101 (proposed rituximab biosimilar)	
Name of Active Ingredient:	Rituximab	

The study will be unblinded at Week 24 and an interim CSR will be prepared based on the 24-week data of all patients. The investigators and patients will remain blinded to treatment assignment during the post Week 24 follow-up period.
 
Sample Size
 
A percentage co-efficient of variation (CV%) ranging from 26.3 to 37.3% for the five co-primary parameters is assumed for this study based on a recent study in RA patients treated with rituximab.
 
When the evaluable sample size in each group is 84, a three group design will have 81% power to reject both the null hypothesis that the ratio of test to standard geometrics means is below 0.800, and the null hypothesis that the ratio of test to standard geometrics means is above 1.250 (i.e., that the test and standard are not equivalent), in favor of the alternative hypothesis, that the means of the two groups are equivalent, assuming that the expected ratio of means is 1.000, the CV% for the standard is 0.330, that data will be analyzed in the log scale using analysis of variance (ANOVA) and that each one sided test is made at the 5% level. Each of the 15 hypotheses tests (five co-primary endpoints × three pairwise comparisons) are powered at 98% to 99.0% to yield 81% study-wide power.
 
Approximately 282 patients (94 patients per group) will be randomized in order to yield a minimum of 84 patients per group to account for a presumed 10% withdrawal.
 
This 94 patients in SAIT101 group and MabThera® group will provide 96% probability of declaring the equivalence in FAS with each one sided test at the 2.5% level, accounting for a presumed 1.0 standard deviation of DAS28 from the REFLEX study, and the equivalence margin of -0.6 to 0.6 chosen as the half of a clinical meaningful improvement of 1.2 in DAS28. Considering 18% withdraw from the REFLEX study, approximately 77 patients per group will provide approximately 91% probability of declaring the equivalence in the PP set.
		

Signatures .....	2
SYNOPSIS.....	3
LIST OF IN-TEXT TABLES .....	15
LIST OF APPENDICES.....	16
LIST OF ABBREVIATIONS AND DEFINITIONS OF TERMS.....	17
1 INTRODUCTION .....	21
1.1 Background .....	21
1.2 Overview of SAIT101 .....	21

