Patients will continue to take their usual prescribed concomitant medications as allowed by the protocol. It is mandatory that doses of all RA medications (MTX, steroids and non-steroidal anti-inflammatory drugs [NSAID]) taken during the first 24-week period must

remain stable (see Section 3.2.5). Patients will also receive an anti-pyretic and an anti-histamine, e.g., paracetamol and diphenhydramine or equivalent, 30 to 60 minutes before each infusion, plus 100 mg i.v. methylprednisone (or its equivalent) at least 30 minutes prior to each infusion.

The study design for individual patients is schematically detailed in Figure 1.

At each visit, blood PK and PD samples should be taken at the same time of day as the start of the first infusion, within a window of  $\pm 10$  minutes of the determined time points of Days 1, 3, 8, 15, 17 and  $\pm 3$  hours at all other time points. All patients will be followed up for safety up to 52 weeks from the start date of the first infusion.

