## **3.2 Treatments**

### **3.2.1 Test Product and Comparator, Dose and Mode of Administration**

SAIT101 is a sterile, clear to opalescent and colorless or a pale yellow, preservative-free solution for i.v. infusion. The formulation of SAIT101 is similar to MabThera® or Rituxan®.

Each patient will be randomized on Day 1 to receive one of three possible treatments (study drug):

- SAIT101: 1,000 mg (10 mg/mL)-Test product;
- Rituxan®: 1,000 mg (10 mg/mL)-Comparator;
- MabThera®: 1,000 mg (10 mg/mL)-Comparator.

All patients received premedication with 100 mg i.v. methylprednisolone (or its equivalent), an antipyretic and an antihistaminic (e.g. acetaminophen and diphenhydramine) per the accepted infusion protocols for rituximab prior to study drug infusions to decrease incidence rate and severity of acute infusion-related reactions.

Since hypotension may occur during rituximab infusion, consideration should be given to withholding anti-hypertensive medications 12 hours prior to the infusion.

The Day 1 infusion rate (both week 0 and week 24) of SAIT101 or MabThera® or Rituxan® will start at 50 mg/hour; after the first 30 minutes, it can be escalated in 50 mg/hour increments every 30 minutes, to a maximum of 400 mg/hour. If there has been no infusion related reaction on Day 1, the Day 15 infusion (both first and second courses) can be infused at 100 mg/hour and increased by 100 mg/hour increments at 30 minute intervals, to a maximum of 400 mg/hour.

The recommended infusion rates are presented in Table 1.

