**Table 5 List of Medications Permitted During the Study**

Treatment	Restriction
Methotrexate	Patients must be taking MTX at a dose of 7.5-25 mg/week (oral or parenteral) throughout the study and for at least 12 weeks prior to study entry. Patients receiving a lower dose of MTX (<10 mg/week) should be doing so as a result of a documented evidence of intolerance to higher doses of MTX. The dose and route of administration should remain stable from 4 weeks prior to randomization and where possible, throughout the entire study period.
Folic or folinic acid	Patients must be taking oral folic or folinic acid or equivalent during the entire study (mandatory co-medication for MTX treatment), according to local standards and availability. The dosing regimen is at the Investigator's discretion.
Antipyretics	Patients will receive an antipyretic, e.g., paracetamol or equivalent, 30 to 60 minutes before each drug infusion.
Antihistamines	Patients will receive an antihistamine, e.g., diphenhydramine or equivalent, 30 to 60 minutes before each drug infusion.
Oral corticosteroids	If receiving current treatment with oral corticosteroids at the time of Screening ( $\leq 10$ mg/day prednisone or equivalent), the dose must remain stable during the 4 weeks prior to Day 1. Increases in corticosteroids for treatment of RA are not allowed over the study period and should be avoided (see Section 3.2.5). Reductions in the dose of corticosteroids will be allowed as clinically required only for safety reasons.
Intravenous or intramuscular corticosteroids	Use of i.v. or intramuscular corticosteroids for RA will be considered worsening of a patient's condition from Baseline and should be recorded as an AE in the eCRF. The only exception will be the administration of 100 mg i.v. methylprednisone or equivalent within 30 minutes before each infusion as part of the study procedures.

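### The protocol times the intravenous steroid premedication at no more than 30 minutes before infusion in two places and at no less than 30 minutes in two others

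*Protocol*

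**What the plan says.** The protocol gives a time window for the intravenous steroid in four places.

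- Synopsis, Treatment Regimen: "100 mg i.v. methylprednisone within 30 minutes prior to each infusion".
- Synopsis, Method of administration: "100 mg i.v. methylprednisone at least 30 minutes prior to each infusion".
- Section 3.1, Summary of Study Design: "100 mg i.v. methylprednisone (or its equivalent) at least 30 minutes prior to each infusion".
- Section 4.3, Table 5, row on intravenous or intramuscular corticosteroids: "100 mg i.v. methylprednisone or equivalent within 30 minutes before each infusion as part of the study procedures".

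Section 3.2.1, which covers dose and mode of administration, mentions the premedication without a window and names the drug differently: "All patients received premedication with 100 mg i.v. methylprednisolone (or its equivalent), an antipyretic and an antihistaminic". It states that the purpose is to make acute infusion-related reactions less frequent and less severe.

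The anti-pyretic and anti-histamine are timed at 30 to 60 minutes before infusion wherever a time is given for them.

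**The concern.** One pair of passages sets an upper limit of 30 minutes between steroid and infusion; the other sets a lower limit of 30 minutes. A site cannot comply with both except at a single instant.

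Three things are at stake.

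- **Conduct.** About 70 centers may each settle the conflict in their own way. Infusion reactions are listed as an adverse event of special interest in Protocol Section 5.4, and SAP Section 16.1 gives them a separate summary. The instruction for the measure meant to limit them should be unambiguous.
- **Deviation records.** Protocol Section 6.12 requires every departure from a protocol requirement to be captured and logged. With two incompatible requirements, a dose given as one section directs can be logged as a departure from another.
- **The Table 5 exception.** That row treats intravenous or intramuscular steroid for RA as a worsening to be recorded as an adverse event, and exempts only the premedication dose given in the shorter window. Read literally, a dose timed as Section 3.1 directs falls outside the exemption. A sensible reader would probably not record an adverse event, because the row concerns steroids given for RA, but the text should not depend on that.

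**Working it through.** The plan states no figure that can be recomputed here, so the check is a comparison of every place that mentions the steroid premedication. Let *t* be the time in minutes from the steroid dose to the start of infusion.

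| Place | Window for *t* | Drug name |
|---|---|---|
| Synopsis, Treatment Regimen | *t* ≤ 30 | methylprednisone |
| Synopsis, Method of administration | *t* ≥ 30 | methylprednisone |
| Protocol 3.1 | *t* ≥ 30 | methylprednisone, or equivalent |
| Protocol 4.3, Table 5 | *t* ≤ 30 | methylprednisone, or equivalent |
| Protocol 3.2.1 | none given | methylprednisolone, or equivalent |
| Protocol 3.6.1 (order of procedures) | none given | not named |
| SAP 12.2 | none given | not named (corticosteroids) |

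1. **Overlap.** The conditions *t* ≤ 30 and *t* ≥ 30 hold together only at *t* = 30. A dose at 20 minutes meets the first and fails the second; a dose at 45 minutes does the reverse.
2. **Does one part of the protocol outrank the other?** A rule that the body prevails over the synopsis does not help. The Synopsis disagrees with itself, and so does the body (Section 3.1 against Table 5).
3. **Does another section settle it?** Section 3.2.1 gives no steroid window. Section 3.6.1 places premedication after the visit assessments but sets no interval. SAP Section 12.2 requires only that premedication comes before the infusion, and lists it.
4. **Is it an extraction fault?** No. All four sentences are complete, and the 30 to 60 minute window for the other two premedications is consistent, so the conflict is confined to the steroid.
5. **Reach.** Part A plans two infusions per patient: 282 × 2 = 564. If every patient were retreated, the ceiling would be 282 × 4 = 1,128. These count planned infusions that the wording governs, not infusions whose timing would actually change. Some patients will stop before completing a course.

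**The case against.** The strongest reply accepts the textual conflict and disputes its consequence.

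- **The places do not carry equal weight.** Table 5 is a list of permitted medication, and its wording defines an exception rather than an administration step. The Method of administration row and Section 3.1 agree with each other. This is fair, but the two Synopsis statements are both instructions and they still conflict.
- **Variation between sites is possible, not shown.** Section 3.2.1 refers to accepted infusion protocols for rituximab, and Section 7.4 leaves more detailed infusion instructions to a Pharmacy Manual that is not available here. That stands: timing may differ by site, and the documents do not show that it will.
- **No estimate changes.** Allocation is randomized and blinded, infusions are given in the same manner in every arm (Protocol 3.5.1), and safety data are summarized without statistical comparison between arms (SAP Section 16). The per-protocol and PK sets turn on deviations that affect efficacy assessments or PK (SAP 4.5 and 4.6), and premedication timing is not among the examples given. All of this stands.
- **The drug name looks like a spelling slip.** Dose and route are the same throughout, and three of the five passages allow an equivalent. This is an editorial matter.

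These points limit the consequence. They do not remove the contradiction, and none of them tells a site which instruction to follow.

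**Conclusion.** The concern holds. Four passages give a steroid window, split two against two; the windows meet only at exactly 30 minutes, and nothing in the protocol or SAP decides between them. This is an internal inconsistency in an operative safety instruction, not a dispute about the design.

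The effect is on conduct and record-keeping. No sample size, power, error rate or analysis set is shown to change, and no bias between arms is expected. The conclusion assumes that no manual outside these documents already imposes one timing. Even if one does, the protocol text would still conflict with itself and should be corrected. The difference in drug name is secondary.

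**What to change.** Reconcile the Synopsis (Treatment Regimen and Method of administration), Section 3.1, Section 3.2.1 and Table 5 so that they state one timing for the steroid premedication and one drug name. State the timing in Section 3.2.1, where sites will look for administration instructions, and have the other places match it or refer to it. In the same edit, word the Table 5 exception so that it covers the premedication as finally timed, and say consistently whether an equivalent steroid is allowed, since neither Synopsis statement mentions one. The clinical choice belongs to the sponsor and is not proposed here.

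The cost is a wording change and a notice to sites, with a check that any site-facing manual agrees. The statistical analysis needs no change. If patients were dosed before the correction, record which timing each site used, so that steroid doses given under either wording are not counted as deviations.
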